We believe TXA has the potential to assist in perioperative control of hemorrhage during burn excision surgery leading to decreased blood loss and smaller transfusion rates. These potential improvements in care may translate into decreased surgical complications and a potential reduction in hospital stay and overall costs.

5. Setting of the Research:

Spectrum Health Butterworth Campus

6. Resources Available to Conduct this Research:

The Spectrum Health Regional Burn Center admits nearly 120 patients each year. Many of these patients require surgical management of their sustained injuries. Study personnel will

include attending burn surgeons and surgical residents with experience in surgical research and knowledge of surgical outcome measures. In addition, the Spectrum Health Office of Clinical Research Operations (OCRO) staff will assist with the informed consent process and subject enrollment, data collection and management, Institutional Review Board (IRB) communication and continuing renewal submission, ongoing subject management, and maintenance of the regulatory files and essential documentation for the study.

7. Study Design:

a. Recruitment Methods

Potential subjects will be recruited during the preoperative period for a planned procedure with any of the burn attending surgeons. A member of the Spectrum Health OCRO will obtain informed consent. This will take place in a private consultation room to ensure privacy and should take approximately 45-60 minutes. In order to minimize coercion, it will be made very clear to patients that their participation is strictly voluntary and that choosing not to participate will in no way affect their care at Spectrum Health.

Study Subjects

Potential subjects include all patients scheduled to undergo burn excision surgery with a deep partial or full thickness burn wound area of at least 350 cm² that meet all of the inclusion criteria, and none of the exclusion criteria. For a procedure to be included within the study, 96 hours must have elapsed since the previous procedure in which the patient was randomized to drug or placebo. If the patient has undergone a procedure outside the scope of this study, the 96-hour waiting period does not apply.

i. Inclusion Criteria

- Subjects undergoing burn excision surgery for standard of care purposes (to include: greater than or equal to 350 cm² of full thickness or deep partial thickness burns)
- Male or female \geq 18 years of age

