- Subject or subject's medical decision maker agrees to participate in this study and provides informed consent

ii. Exclusion Criteria

- Subjects with a history of hypercoagulopathy, deep vein thrombosis or pulmonary embolism
- Baseline creatinine level greater than 2.83 mg/dL
- Subjects with known hypersensitivity to tranexamic acid
- Patients with acquired defective color vision
- Patients with subarachnoid hemorrhage
- Children
- Pregnant women
- Prisoners

b. Study Endpoints

The primary outcome measures will be operative blood loss (measured and calculated) and red blood cell transfusion rates in subjects undergoing the eligible procedures. Secondary outcome measures will include total hospital length of stay, wound complication, transfusion reactions, and skin graft survival.

c. Procedures Involved in the Research

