The study design will be a randomized, double-blinded, placebo-controlled trial, with the randomization to occur on a per procedure basis. Following satisfaction of inclusion/exclusion criteria and enrollment into the study by the Spectrum Health OCRO research staff, the subject and each procedure the patient undergoes will be assigned a study number. A single consent will be obtained for randomization of each procedure that a patient may undergo meeting inclusion criteria for the study. A single study participant could potentially be randomized to both treatments of the study if that participant undergoes two or more procedures. Each procedure a participating subject undergoes will be randomized based on a predetermined randomization schedule, created by an independent statistician at Grand Rapids Medical Education Partners (GRMEP) research department. The randomization schedule will be held by the pharmacists and checked prior to each procedure to determine the appropriate treatment (placebo or TXA). Surgical timing will be coordinated with the OCRO. The study participants will receive preoperative intravenous TXA or Normosol as placebo treatment. The preparation will be indistinguishable by nursing, surgical, or anesthesia staff. The TXA procedures will receive a 1000 mg dose immediately preceding surgical incision administered by the anesthesia provider, while the placebo procedures will receive an equivalent volume of Normosol. The dose will be administered via intravenous piggyback over 15 minutes. Operative details will be recorded including procedure performed, IV fluids received, estimated blood loss, lowest recorded body temperature, and transfused blood products. Perioperative hemoglobin level data will also be collected. Standard daily laboratory measurements will continue unless clinical conditions necessitate more frequent monitoring, per standard practice. Transfusion will take place for hemoglobin levels < 7.0 g/dL or hemoglobin level < 10 g/dL with clinical symptoms indicating need for transfusion, per standard practice. Final decision on transfusion will be made according to the staff surgeon's discretion.

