It is anticipated that each patient will receive an average of three major surgical procedures during the treatment of their burn injury. The number of procedures may range from a single procedure to greater than 6 procedures for an individual patient depending on the extent of their injury. The time between subsequent procedures typically ranges from ten days to several weeks. Prior to each procedure, the patient will be re-randomized to receive TXA or placebo.

Data to be recorded includes patient demographics (age, sex, height, weight), burn injury characteristics (total body surface area, location, depth of burn), hospital admission date, hospital discharge date, past medical history, past surgical history, medications, and laboratory values. Data from operative records will include procedure date, procedure performed, wound measurements, lowest body temperature, operative blood loss, operative time, amount of fluid received, and intraoperative transfusion requirements. Postoperative data to be collected includes hemoglobin and hematocrit levels, transfusion requirements, surgical complications, skin graft survival (%), thromboembolic events, and length of hospital stay.

d. Data Management

The Spectrum Health OCRO research staff will collect outcome data at the time of each surgical procedure. Data will be stored in a password-protected REDCap

database. The OCRO will also keep a secure record of the procedures randomized to the TXA and placebo arms, which will be blinded from the study personnel.

e. Provisions to Monitor the Data for the Safety of Subjects

Adverse events including infections, allergic reactions, graft loss, respiratory failure, anaphylaxis, thromboembolic events and development of acute renal failure will be monitored and recorded at the time of occurrence by the Spectrum Health OCRO research staff. In the event an increased number of unanticipated events occur, the study will be temporarily stopped pending review. A review of unblinded data will be performed by an independent clinician and statistician at Grand Rapids Medical Education Partners to determine the need to discontinue or resume the study. If a significant increase in adverse events is noted in the treatment arm related to the study drug, the trial will be terminated. Decisions resulting from the review will be discussed with the primary investigator.

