Interim reviews of unblinded data for statistically significant findings will be performed by an independent clinician, pharmacist, and statistician after the first 80 procedures have been completed. Findings will be reviewed with the investigators, and decisions will be made as to whether or not the research study continues. These interim reviews and outcomes will be reported to the IRB.

f. Withdrawal of Subjects

Subjects will be withdrawn from the study if they experience an adverse drug reaction defined as anaphylaxis. Other potential side effects such as nausea, vomiting, or diarrhea will be treated symptomatically per standard of care. If refractory to standard treatment for these side effects, subjects will be withdrawn from the study. Subjects experiencing any thrombotic event prior to completion of study drug dosing schedule will be withdrawn from study. Subjects may choose at any time to voluntarily withdraw from the study. If subjects choose to withdraw, No further data will be collected. Data already collected will be included in the study.

The primary investigator may remove a subject at any time from this research study if it is felt to be in the best interest of the subject.

8. Statistical Plan

a. Sample Size Determination

The primary outcome variable for the study is transfusion following a procedure. The analysis will be performed using generalized estimating equations (GEEs), as each individual may have multiple surgical procedures that may be randomized to either the control or TXA treatment prior to EACH procedure. An initial assessment for sample size for a McNemar test, assuming that the transfusion rate following a control procedure is 50%, the rate following a TXA procedure is 30%, $\alpha = 0.05$ and $\beta = 0.20$, indicates that 61 subjects would be needed. The control transfusion rate is based upon previous data at Spectrum Health, while the difference of 20 percentage points is based upon our estimate of what constitutes a clinically important effect. Due to the use of GEE for the analysis, a correction factor is needed.¹⁷ From previous data from the Spectrum Health Burn Unit, we assume that there will be three procedures per patient. If we further assume that the intraclass correlation coefficient = 0.8 (postulated correlation of repeated measurements), we will be able to show a statistically significant effect with 53 subjects. With an average of 3 procedures per patient, the total procedures will be 159.

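### Section 7e takes the unblinded interim findings to the investigators, who probably include surgeons with discretion over transfusion, without limiting them to a recommendation

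*Combined protocol and SAP*

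**What the plan says.** Section 7e describes two unblinded reviews.

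The scheduled one reads: "Interim reviews of unblinded data for statistically significant findings will be performed by an independent clinician, pharmacist, and statistician after the first 80 procedures" are complete. It continues: "Findings will be reviewed with the investigators, and decisions will be made as to whether or not the research study continues". Then: "These interim reviews and outcomes will be reported to the IRB". Nobody is named as taking the decision, and the IRB is given a report but no stated role in deciding.

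The other review is triggered by an excess of unanticipated events. There an independent clinician and statistician determine whether the study stops or resumes, and "Decisions resulting from the review will be discussed with the primary investigator".

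Section 7b lists as primary outcome measures "operative blood loss (measured and calculated) and red blood cell transfusion rates in subjects undergoing the eligible procedures". Section 8a, which sets the sample size, names transfusion after a procedure as the primary outcome variable. Section 7c gives two hemoglobin criteria for transfusion and then adds: "Final decision on transfusion will be made according to the staff" surgeon's judgement.

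**The concern.** Where an outcome depends partly on clinical judgement, comparative interim results are best kept from those who exercise that judgement. Here the text takes the findings of an unblinded look to the investigators and sets no limit on their content.

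A surgeon who learns that tranexamic acid (TXA) looks effective, or ineffective, still does not know what the next patient received. The surgeon may nevertheless become more or less ready to transfuse in the range where judgement applies. Section 8a plans on transfusion rates of 50% (control) and 30% (TXA). A general change in practice could move both rates away from these values and shrink the difference. Procedures before and after the look would then differ for reasons unrelated to treatment, and the pooled transfusion comparison would be harder to interpret.

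**Working it through.** **1. Where the look falls.** The inputs are in section 8a: 61 subjects from the McNemar calculation, m = 3 procedures per patient, and an intraclass correlation (ICC) of 0.8. The plan does not print its correction formula, but the usual one for repeated measurements reproduces its figure:

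- N × [1 + (m − 1) × ICC] / m = 61 × (1 + 2 × 0.8) / 3 = 61 × 2.6 / 3 = 52.87, rounded up to 53 subjects
- 53 × 3 = 159 procedures
- Position of the look: 80 / 159 = 0.503
- Procedures after it: 159 − 80 = 79, and 79 / 159 = 0.497

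The 79 is an upper limit on exposure, because the trial may stop at the look and procedures may go on while the review is under way. It counts procedures, not new patients. One consent covers all of a patient's qualifying procedures (section 7c), so some of the 79 may belong to patients enrolled before the look.

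**2. What is passed on.** In the scheduled review the reviewers search unblinded data for significant findings, and the next sentence takes *findings* to the investigators. In the triggered safety review, decisions are what is discussed, and only with the primary investigator. So 7e already contains a narrower wording and does not use it for the scheduled review. No other section narrows it.

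**3. Who hears it.** The protocol does not define the investigators. Section 6 says study personnel "include attending burn surgeons and surgical residents with experience in surgical research and knowledge of surgical outcome measures". Section 7a says: "Potential subjects will be recruited during the preoperative period for a planned procedure with any of the burn attending surgeons". It is therefore likely, though not stated, that some of those told are surgeons who operate on trial patients.

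**4. How much discretion they have.** One of the two transfusion criteria in section 7c combines a hemoglobin level with clinical symptoms, which calls for judgement, and the staff surgeon has the last word in any case.

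**5. What the existing safeguards cover.** Pharmacists hold the randomization schedule and the preparations cannot be told apart (section 7c). The record of allocations is kept from study personnel (section 7d). These measures protect the allocation of each procedure. None of them deals with knowledge of the interim comparison between arms.

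No size of bias can be computed. The documents do not say how practice would change, or in which direction.

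**The case against.** The strongest reply is that the randomized comparison is not threatened. Each later procedure is newly randomized, and a surgeon blinded to allocation applies any change of habit to both arms. A shift over calendar time is shared by the arms and does not by itself favour one of them. The hemoglobin criteria also limit how far practice can move. All of this stands, and it reduces the point to one about conduct, event rates and dilution.

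Case selection is also a weaker route than it first seems. Section 7a makes all scheduled patients who meet the criteria potential subjects. Staff of the Office of Clinical Research Operations (OCRO) obtain consent and enroll, and one consent carries over to later procedures. Surgeons still plan the operations and could influence referral, so this route is narrow but not closed.

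In a trial described as double-blinded, *findings* may mean no more than the reviewers' conclusion. That is possible. The same word in the preceding sentence refers to significant results from unblinded data, however, and nothing excludes arm-level estimates. If only a conclusion was meant, the amendment costs nothing.

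A reader might infer that surgeons will be unblinded to individual procedures, or that about half of the trial would be biased in favour of TXA. The documents support neither. Later assignments stay concealed, and 79 of 159 is only the share of procedures after the look.

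**Conclusion.** The point holds as a cheap improvement of minor severity. The scheduled interim review takes its findings to the investigators with no limit to a recommendation, in a trial whose primary outcome is partly at the staff surgeon's discretion. At most 79 of 159 procedures (49.7%) would follow the look.

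The risk depends on three conditions that the documents leave open: that what is shared shows the direction or size of the effect, that those told include operating surgeons, and that the trial continues. The first two are plausible on the wording, but neither is established. It should not be read as a planned disclosure of arm-level results to every treating surgeon.

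That no decision-maker is named is a secondary matter. On its own it would be missing detail.

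**What to change.** In section 7e, replace the sentence on reviewing findings with the investigators by:

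> The independent clinician, pharmacist and statistician will give the investigators only a recommendation to continue or stop; arm-level interim results will not be shared with investigators or with staff who treat, enroll or assess subjects until database lock.

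Replace the sentence on IRB reporting that follows by:

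> The reviewers will report the interim review and its outcome directly to the IRB, and any arm-level results in that report will not pass through the investigators.

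The second change is needed because the current sentence leaves the route of the report open. Section 6 has OCRO staff assist with IRB communication, and they also enroll subjects and collect data, so the first replacement sentence keeps arm-level results from them too. As a secondary clarification, the sponsor should name who acts on the recommendation. The triggered safety review is unchanged.

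The cost is two sentences, and the three reviewers are already planned. The drawbacks are that whoever decides acts without seeing comparative results, and that a bare recommendation to continue still conveys limited information. It would, however, hide the direction and size of the effect.

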b. **Statistical Methods**

Summary statistics will be calculated. Quantitative data will be expressed as the mean±SEM and nominal data will be expressed as a percentage. Comparisons between groups for quantitative variables will be performed using the t-test. Nominal variables will be evaluated using the χ^2 test. The relationship between TXA administration and transfusion will be determined using GEE. Significance will be assessed at $p<0.05$. Analyses will be performed using intention to treat.

9. Risks to Subjects

TXA is an FDA approved medication. The safety of TXA has been demonstrated in a meta-analysis of the off-label use of TXA in the perioperative period. A theoretical risk of thromboembolic events exists, though no significant adverse outcomes have been reported with the proposed dosing schedule. Reported side effects include nausea, vomiting, diarrhea, and dizziness. Uncommon side effects include allergic dermatitis, giddiness, and hypotension. Rare side effects include blood clots, convulsions, and visual changes.

10. Potential Benefits to Subjects

Potential benefits include decreased surgical blood loss resulting in decreased transfusion requirements. Transfusion of packed red blood cells has been associated with numerous potential adverse events. In addition, decreased overall hospital cost may occur if the study subjects experience decreased complication rates.

11. Provisions to Protect the Privacy Interests of Subjects

The study, potential risks and benefits of treatment will be discussed extensively with each potential subject preoperatively in a private space. Any questions they have will be answered accordingly. Reported data will not contain identifiable information. Patient consent and all other research related activities will take place in a private exam room.

12. Provisions to Maintain the Confidentiality of Data

Identifiable study data will be kept in a secure password-protected file or locked cabinets by the Spectrum Health OCRO. The Spectrum Health OCRO will have record of the randomization of each individual subject stored in a controlled, secure area.

13. Medical Care and Compensation for Injury

Any medical or surgical complications experienced relative to this research will be treated in accordance with current standards of care. No study funds have been set aside to compensate subjects for injury.

14. Cost to Subjects

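### The 53 patients / 159 procedures rest on a correction factor for a treatment held constant within a patient, but this trial re-randomizes every procedure, so the stated beta of 0.20 is unsupported

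*Combined protocol and SAP*

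**What the plan says.** Section 8a starts from a McNemar calculation at 50% (control) against 30% (TXA), alpha 0.05 and beta 0.20, which "indicates that 61 subjects would be needed". It continues: "Due to the use of GEE for the analysis, a correction factor is needed", citing a textbook without printing the formula. The cluster size comes next: "From previous data from the Spectrum Health Burn Unit, we assume that there will be three procedures per patient". The correlation is postulated: "If we further assume that the intraclass correlation coefficient = 0.8 (postulated correlation of repeated measurements". The conclusion is "we will be able to show a statistically significant effect with 53 subjects", or 159 procedures in all.

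On the design, section 7c says: "Prior to each procedure, the patient will be re-randomized to receive TXA or placebo". It also says: "The number of procedures may range from a single procedure to greater than 6 procedures for an individual patient". On the analysis, section 8b says only: "The relationship between TXA administration and transfusion will be determined using GEE". It gives no link function, working correlation or standard error.

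**The concern.** Repeated procedures in one patient can help or hurt precision, depending on whether treatment changes within the patient. If a patient stays on one arm, correlated results are partly redundant and more patients are needed as correlation grows. If treatment is re-randomized each time, part of the comparison is made within patients, and correlation can reduce the number needed. The adjustment in 8a moves in the first direction; the design in 7c is of the second kind.

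What is at stake is the power statement for transfusion, which 8a names as the primary outcome variable. If the step from 61 to 53 does not fit the design, the protocol cannot say what power 159 procedures provide, and a null result would be hard to interpret. Whether correlation helps also depends on the GEE working correlation. Section 7e schedules an unblinded review after 80 procedures, so that choice should be fixed before then.

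**Working it through.** **Inputs.** From 8a: rates of 50% and 30%, alpha 0.05, beta 0.20, base 61, m = 3 procedures per patient, ICC 0.8, result 53 patients and 159 procedures. From 7c and 8a: treatment is randomized at each procedure. Assumed, because the plan does not say: two-sided test, 1:1 allocation, no procedures lost, and the full 0.05 available for transfusion.

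**1. The plan's own figure.** 61 × [1 + (3 − 1) × 0.8]/3 = 61 × 2.6/3 = 52.87, rounded up to 53; 53 × 3 = 159. The match is exact, but the formula is inferred, since the plan prints none.

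**2. What that factor describes.** [1 + (m − 1)r]/m is the variance of the mean of m equally correlated results from one patient, relative to a single result. It applies when all of a patient's results belong to one arm.

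**3. The factor for re-randomization.** With each procedure randomized independently and exchangeable weighting, the variance relative to the same number of independent procedures is (1 − r)(1 + (m − 1)r)/(1 + (m − 2)r). For m = 3 this is (1 − r)(1 + 2r)/(1 + r). Independent procedures need 93 per arm, 186 in all, for 80% power. Multiplying 186 by the factor gives:

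| r (binary scale) | Patients by the plan's factor | Re-randomization factor | Procedures needed | Patients needed |
|---|---|---|---|---|
| 0 | 20.3 → 21 | 1.000 | 186 | 62 |
| 0.3 | 32.5 → 33 | 0.862 | 161 | 54 |
| 0.4 | 36.6 → 37 | 0.771 | 144 | 48 |
| 0.53 | 41.9 → 42 | 0.633 | 118 | 40 |

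The two patient columns run in opposite directions. At r = 0 the plan's factor would accept 21 patients, or 63 procedures, where 186 are needed.

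**4. The base of 61.** The McNemar size is n = (z₁₋α/₂√ψ + z₁₋β√(ψ − d²))²/d², with d = 0.20 and discordance ψ = 0.5 − 2φ√(0.25 × 0.21). Independent pairs (φ = 0) need 95.7, or 96. A size of 61.0 arises at φ = 0.386 (ψ = 0.323). With a continuity correction, φ = 0.5 gives 60.3, or 61; one-sided and uncorrected, φ = 0.20 gives 61.0. The plan states none of these, but on each reading the 61 already credits a positive pair correlation. The base thus presumes that treatment varies within a patient, and the factor applied to it presumes that it does not.

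**5. The scale of 0.8.** Two procedures with rates 50% and 30% can both end in transfusion at most 30% of the time. The largest binary correlation is (0.30 − 0.15)/√(0.25 × 0.21) = 0.655, so 0.8 cannot hold between a control and a TXA procedure on that scale. A latent-normal correlation of 0.8 is possible. It corresponds to binary 0.530 for control–TXA, 0.590 for control–control and 0.577 for TXA–TXA pairs.

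**6. Power of 159 procedures.** By formula, 79.5 independent procedures per arm give 73.5%. The table is from simulated logistic GEE with robust standard errors and latent-normal data, 4,000 to 10,000 data sets per setting. The z columns are for 53 patients with three procedures each. The corrected range covers two small-sample corrections (t, patients minus 2 df) and also assumed cluster sizes of 1 to 8 totalling 159.

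| Control–TXA correlation | Exchangeable, uncorrected z | Exchangeable, small-sample corrected | Independence, uncorrected z |
|---|---|---|---|
| 0 | about 75% | 70–73% | 74–75% |
| 0.3 | about 81% | 77–79% | about 74% |
| 0.4 | about 85% | 81–83% | about 73% |
| 0.53 | about 92% | 89–91% | about 72% |

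Uncorrected type I error under the exchangeable structure, at 50% in both arms, was 5.4–6.3%; corrected, 4.4–5.3%.

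**The case against.** The strongest reply is that the number may be adequate even if its derivation is not. Reading 0.8 as a latent correlation and using an exchangeable GEE, 159 procedures give about 89–92%, above the planned 80%. That stands. A reader might infer from the misapplied factor that the trial is underpowered or needs more patients; the documents do not support this, because power depends on a correlation scale and a working structure that they leave open.

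The formula is also an inference from one number, and the cited textbook was not consulted. That stands as a limit on what can be said of the authors' intent. It does not rescue the result: whatever formula was used, the plan shows no calculation of power for per-procedure randomization, and a binary 0.8 between arms is impossible. Nor is there a slip in the arithmetic, which reproduces exactly. The fault lies in the method and the missing specification.

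Finally, a reader might take the silence of 8b to mean that independence is as likely as exchangeable. That goes too far. Section 8a introduces GEE because of repeated procedures and postulates a single correlation among them, which leans towards exchangeable. It does not exclude independence.

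**Conclusion.** The point holds as a gap in justification and pre-specification that should be fixed. The 53 and 159 match a factor for a treatment constant within a patient, applied to a base that already credits pairing, in a trial that re-randomizes each procedure. The 0.8 has no stated scale. The stated beta of 0.20 is therefore not supported, but neither is a claim of inadequate power. Under an exchangeable GEE with uncorrected robust z, power runs from about 75% at correlation 0 to about 92% at 0.53. At 0.53 the unnamed working correlation alone accounts for about 20 points (92% against 72%).

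These figures assume 50% against 30%, a two-sided 0.05 test, 1:1 allocation, a common latent-normal patient effect, no lost procedures, and no alpha spent at the 80-procedure review (7e) or shared with blood loss, which 7b also lists as primary. The plan has not settled the two alpha questions. Confidence is high on the arithmetic and the mismatch with the design; the authors' actual formula remains inferred.

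**What to change.** Keep 159 procedures.

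- **Section 8a.** Replace the McNemar 61, the correction factor and the unscaled 0.8 with power for 1:1 randomization of each procedure, 50% against 30%, two-sided 0.05, exchangeable GEE. Tabulate it by binary-scale control–TXA correlation: about 75% at 0, 81% at 0.3, 85% at 0.4 and 92% at 0.53 (latent ICC 0.8) with uncorrected robust z; or 70–73%, 77–79%, 81–83% and 89–91% with a small-sample correction.
- **Conditions, also in 8a.** State that these figures hold only if no alpha is spent at the 80-procedure review, none is shared with blood loss and no procedures are lost. Mark these as open conditions, not decisions.
- **Section 8b.** Before unblinded data are reviewed, specify GEE with logit link, exchangeable working correlation and robust standard error. A small-sample correction is optional; the power quoted in 8a should match the choice.
- **Correlation.** If the earlier Burn Unit data contain repeat procedures, estimate the correlation from them. If those procedures were without TXA, they give control–control pairs: 0.32, 0.43 and 0.59 there correspond to 0.3, 0.4 and 0.53 between arms under a latent-probit model.

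The cost is one rewritten paragraph and one added sentence, with no more patients. The downside is that stated power becomes dependent on the correlation and falls below 80% when it is low; the optional correction takes off about 2–4 points.

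### Section 8b reports quantitative data as mean±SEM with no allowance for repeated procedures in one patient, so each arm mean would look more precise than it is

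*Combined protocol and SAP*

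**What the plan says.** Section 8b sets the summary format and the test for quantitative variables: "Quantitative data will be expressed as the mean±SEM", and "Comparisons between groups for quantitative variables will be performed using the t-test". The only method there that handles repeated procedures is reserved for one outcome: "The relationship between TXA administration and transfusion will be determined using GEE".

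The unit being compared is the procedure. Section 7c describes a trial "with the randomization to occur on a per procedure basis" and adds: "A single study participant could potentially be randomized to both treatments of the study if that participant undergoes two or more procedures". On numbers, section 8a says "we assume that there will be three procedures per patient", uses an "intraclass correlation coefficient = 0.8 (postulated correlation of repeated measurements" and concludes: "With an average of 3 procedures per patient, the total procedures will be 159". Section 7c also expects the count per patient to vary, from one to more than six.

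Three things are not stated: whether the SEM is taken over procedures or over patients, the allocation ratio, and any within-patient correlation for blood loss, hemoglobin, operative time or another quantitative variable.

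**The concern.** An ordinary SEM divides the SD by the square root of the number of observations and is correct only if those observations are independent. Here an arm is a set of procedures, and several may come from the same patient. Section 8a accepts that such results are correlated, but section 8b prescribes a precision statistic that ignores it. An error bar that is too short would then sit beside each arm mean, including operative blood loss, which section 7b lists among the primary outcome measures.

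The comparison has a second, separate weakness. The unadjusted t-test makes no use of the fact that many patients would contribute to both arms, so it discards precision that the design provides.

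**Working it through.** **1. The plan's own figure.** Section 8a starts from 61 subjects and corrects for three procedures and a correlation of 0.8: 61 × (1 + 2 × 0.8)/3 = 52.87, rounded up to 53; 53 × 3 = 159. The plan's figures reproduce. The 0.8 enters only here, in a calculation for transfusion.

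**2. Error of an arm mean, three procedures each.** Assume 1:1 allocation, independent for each procedure, and an SEM over procedures. Let m be the number of a patient's procedures that fall in a given arm, so m is Binomial(3, 0.5).

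- Design effect = 1 + ρ × E[m(m−1)]/E[m]
- E[m] = 1.5 and E[m(m−1)] = 3 × 2 × 0.25 = 1.5, so the ratio is 1 and the design effect is 1 + ρ
- Shortfall of the SEM = 1 − 1/√(design effect)

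| Correlation ρ | Design effect | True SE ÷ SEM | SEM too small by |
|---|---|---|---|
| 0.3 | 1.3 | 1.14 | 12% |
| 0.5 | 1.5 | 1.22 | 18% |
| 0.8 | 1.8 | 1.34 | 25% |

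A simulation of 53 patients with three procedures each (20,000 runs, unit variance, ρ = 0.8) gave a mean SEM of 0.111 against a true SE of 0.151, a shortfall of 26%.

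**3. Unequal counts.** If k is a patient's number of procedures, the design effect under 1:1 allocation is 1 + ρ × 0.5 × E[k(k−1)]/E[k]. The plan gives no distribution for k, so two were assumed, both at ρ = 0.8:

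- Uniform on 1 to 5 (mean 3): E[k(k−1)] = 8, design effect 1 + 0.4 × 8/3 = 2.07, shortfall 30%.
- Skewed on 1 to 7, with probabilities 0.28, 0.22, 0.16, 0.12, 0.09, 0.07 and 0.06 (mean 2.97): E[k(k−1)] = 9.26, design effect 1 + 0.4 × 9.26/2.97 = 2.25, shortfall 33%.

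**4. The between-arm difference.** In the simulation of step 2, the ordinary SE of the difference was 0.157 and the true SE 0.157. The t-test rejected in 5.0% of null trials. A patient's shared component adds error to both arm means, but under per-procedure randomization it largely cancels in the difference.

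**5. Precision lost by not modelling the patient.** With 159 procedures the unadjusted SE is √(1/79.5 + 1/79.5) = 0.159. For a model with exchangeable correlation and three procedures each, the expected information per patient is 0.75 × (1 + ρ)/[(1 − ρ)(1 + 2ρ)], and SE = 1/√(53 × information).

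- ρ = 0.3: information 0.871, SE 0.147
- ρ = 0.5: information 1.125, SE 0.130
- ρ = 0.8: information 2.596, SE 0.085

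Simulation gave 0.146, 0.129 and 0.085, against about 0.158 unadjusted.

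**The case against.** The strongest reply is that nothing the trial concludes would change. Transfusion, which section 8a calls the primary outcome variable, is analysed by GEE, and the t-test for quantitative variables keeps its error rate. Readers of a two-arm trial mostly use arm-wise SEMs to compare the arms, and for that the ordinary SEMs are nearly right at ρ = 0.8: √2 × 0.111 = 0.157, which matches the true SE of the difference. Two corrected arm SEs of 0.150 combined the same way give 0.212, about a third too large. This stands. It means that inflating the arm-wise SEMs is not the remedy. It does not rescue the SEM as a measure of an arm mean's precision, and it does not recover the precision lost in step 5.

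A second reply is that 0.8 was postulated for a yes/no outcome, which section 8b reports as a percentage. Blood loss may correlate less within a patient, because section 4 ties it to the area debrided and that area can differ between procedures. This also stands, and it is why the size is given as a range. The shortfall disappears only if a patient's procedures are uncorrelated.

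A third is that SD versus SEM is partly a matter of reporting preference. That is fair, and SDs would be good practice without any clustering.

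**Conclusion.** The point holds as a minor matter of reporting and efficiency. If the SEM is taken over procedures with 1:1 allocation, it understates the error of each arm mean by about 12% to 25% for correlations from 0.3 to 0.8 with three procedures each, and by about 30 to 33% at 0.8 under the assumed unequal counts. The unit of the SEM, the allocation ratio, the correlation for quantitative variables and the count distributions are all assumptions.

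A reader might infer three stronger things that the documents do not support:

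- That the plan itself implies error bars 25% too narrow. It does not: it fixes no correlation for any quantitative variable.
- That the t-tests would give false positives. Under per-procedure randomization they do not; they are valid but inefficient.
- That patient-level values such as age or burn size will be counted once per procedure. The plan specifies no such table. If one were made, ρ would be 1 for those values and the SEM would be 29% too small (1 − 1/√2).

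**What to change.** In section 8b and the table shells:

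- Describe procedure-level quantitative data with mean and SD, or median and quartiles, in place of mean and SEM.
- Report the treatment difference for blood loss and the other procedure-level quantitative outcomes with a 95% CI from a patient-clustered model: GEE with exchangeable correlation, or a mixed model. This extends to these outcomes the approach already planned for transfusion.
- If patient-level variables such as age or burn size are tabulated, summarise them once per patient, and state the unit of each table.

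The cost is a small amount of extra analysis and wording. Sample size, data collection and trial conduct are unaffected.
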